8 STUDY ASSESSMENTS AND PROCEDURES

8.1 ENDPOINT AND OTHER NON-SAFETY ASSESSMENTS

Variables and Their Measurement	Respondent	Time 1	Time 2	Time 3
Short Acculturation Questionnaire for Hispanics	Mother	X		
Health History Questionnaire	Mother	X		
Sports Physical	Mother	X		
Adiposity (Primary Outcomes)				
Waist Circumference	Mother/Child	X	X	X
Triceps and Subscapular Skinfolds	Mother/Child	X	X	X
Weight Status (Primary Outcomes)				
Height/Weight	Mother/Child	X	X	X
BMI/BMI Percentile	Mother/Child	X	X	X
Health Behavior				
Adult Health Behavior Survey	Mother	X	X	X
Health Promoting Lifestyle Profile II	Mother	X	X	X
24-hour Food Recall for 3 days	Mother for Self/Child	X	X	X
Accelerometer for 7 days	Mother for Self/Child	X	X	X
Self-Efficacy				
Eating Self-Efficacy Scale	Mother	X	X	X
Exercise Self-Efficacy Scale	Mother	X	X	X
Demographic Data	Mother for Self/Child	X		
Health History Update Questionnaire	Mother for Self/ Child		X	X
Process Evaluation Bi-Monthly	Project Manager			
Exit Interviews	Mother			X

Time 1 (0 months [baseline]); Time 2 (9 months [completion of the intervention]); Time 3 (15 months [after 6 months with no contact from the study staff]).

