9 STATISTICAL CONSIDERATIONS

9.1 STATISTICAL HYPOTHESES

Aim 1: Test the efficacy of the intervention in slowing adiposity and weight gain trajectory and improving health behaviors (nutrition and physical activity) in 4-year-old Hispanic children from Time 1 (0 months [baseline]) to Time 2 (9 months [completion of the intervention]) and Time 1 to Time 3 (15 months [after 6 months with no contact from the study staff]).

Aim 2: Test the efficacy of the intervention in decreasing adiposity and weight and improving health behaviors and self-efficacy in overweight or obese Hispanic mothers from Time 1 to Time 2 and from Time 1 to Time 3.

Primary outcomes include slowing of child adiposity (waist circumference and triceps and subscapular skinfolds) and weight gain (BMI percentile) trajectory and a decrease in mother's adiposity and weight (BMI). We hypothesize that intervention group children will slow the trajectory of adiposity and weight gain and intervention group mothers will decrease adiposity and weight significantly more than the control group.

Secondary outcomes include child and mothers health behaviors (nutrition and physical activity) and mother's self-efficacy (nutrition and physical activity). We hypothesize that intervention group children and mothers will improve health behaviors and mothers will improve self-efficacy significantly more than the control group.

Aim 3: Identify the mediators through which the intervention influences the trajectory of adiposity and weight gain in children and decrease in adiposity and weight in mothers. We hypothesize that health behaviors and self-efficacy may mediate adiposity and weight loss in mothers and nutrition and physical activity behaviors in children may mediate a slower adiposity and weight gain trajectory.

Aim 4: Calculate the cost of implementing the intervention for public health departments and the costs for mothers participating, from Time 1 to Time 2 and compare these costs to the outcomes of the intervention (cost-effectiveness) and the potential economic benefits of these outcomes (cost-benefit analysis). We hypothesize that the intervention is primarily focused on knowledge and behaviors in an at-risk population and may be cost-effective in comparison with other approaches to managing overweight and obesity.

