9.2 SAMPLE SIZE DETERMINATION

A total of 250 mother-child dyads, or 125 dyads in each randomized group, are expected to complete the study. However, we will enroll 294 mother-child dyads ($n = 588$ participants) or 147 dyads per group, to take into account a 15% attrition rate. Our previous studies with Hispanic mothers with limited English proficiency and their children have had attrition rates ranging from 9% to 15% [23, 33]. Power calculations were performed with POWERLIB20 SAS/IML modules, which incorporate methods described in Muller [39]. These methods calculate power for a general linear multivariate model that includes repeated measures data structures, of which a two-group longitudinal design is a special case. Power was calculated on the use of a separate multivariate model for each outcome addressed in the aims, incorporating measurements at all available time points. Effect size estimates were based on the pilot data [23], where estimated within-subject correlation and standardized mean difference were .25 and .53, respectively, for mothers' BMI and .30 and .59, respectively, for children's BMI percentiles. For each outcome, power was computed for a test of the time by treatment interaction at a two-sided significance level of .05. For an analyzable sample of 125 mother-child dyads per group (total of 250 mother-child dyads), calculated statistical power exceeds 95% for both the test of children's BMI percentiles in Aim 1 and the test of mothers' BMI in Aim 2; if the within subject correlations and standardized mean differences are lower than observed in the pilot at .20 and .45, respectively, statistical power will nonetheless exceed 80%. A formal power analysis was not conducted for Aim 3 because the focus is on estimation (rather than testing) of direct and indirect mediation effects. Nonetheless, based on Shrout and Bolger [40], a sample size of 80 to 85 should provide power in the 70% to 85% range to detect medium effects of the intervention on the mediator (e.g., maternal self-efficacy), and the mediator on the outcomes (e.g.,

mother's BMI) with a two sided .05 significance level. Our 250 dyads should provide an adequate sample to quantify mediation of the relevant variables.

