9.4 STATISTICAL ANALYSES

- 9.4.1 GENERAL APPROACH
- 9.4.2 ANALYSIS OF THE PRIMARY ENDPOINT(S)
- 9.4.3 ANALYSIS OF THE SECONDARY ENDPOINT(S)
- 9.4.4 SAFETY ANALYSES
- 9.4.5 BASELINE DESCRIPTIVE STATISTICS
- 9.4.6 PLANNED INTERIM ANALYSES
- 9.4.7 SUB-GROUP ANALYSES
- 9.4.8 TABULATION OF INDIVIDUAL PARTICIPANT DATA
- 9.4.9 EXPLORATORY ANALYSES 9.5
- 9.4.10 DATA ANALYSIS

Aim 1: To test the efficacy of the intervention in decreasing trajectory of adiposity and weight gain in 4-year-old children, separate mixed models will be used to test longitudinal differences between the intervention and control group means for each outcome across the study period. Mixed effects models, with a random intercept to account for between-mother or between-child differences, will be used for repeated measures analyses of each outcome (child BMI percentile, waist circumference, and triceps and subscapular skinfolds). The dependent variable will be the outcome at each of the three time points; the model will include time point (categorical), intervention group, and the interaction between the two. A test of this interaction will serve as the overall test of intervention effect, and step-down tests will be conducted to compare Time 2 and Time 3 to Time 1, and to estimate how or whether the intervention effect changed from Time 2 to Time 3, using a Hochberg correction to account for multiple comparisons [41, 42]. Results will be summarized through the least-squares means for each group at each time point and the mean difference and corresponding 95% confidence interval.

Aim 2: To test the efficacy of the intervention in decreasing adiposity and weight in mothers, we will fit mixed models analogous to those described for Aim 1 with each of the primary outcomes (mother's BMI and adiposity measures: waist circumference, and triceps and subscapular skinfolds) and secondary outcomes (child health behaviors: nutrition and physical activity, mother's health behaviors: nutrition and physical activity, and mother's self-efficacy: nutrition and physical activity).

Aim 3: To identify the mediators through which the intervention influences weight management in mother-child dyads, the approach of Shrout and Bolger [40] will be employed. This method, based on bootstrapping, builds on established mediation testing procedures, such as the Baron and Kenny approach [43] and the Sobel test [44]. Mediation analyses test pathways by which an explanatory variable (X) is theorized to influence the

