mediator (M), which in turn influences the outcome (Y). Models will be conceptualized for each measure of weight and adiposity for mothers identified in Aim 1 (Y) and for each proposed mediator (M), relative to the randomized intervention group (X). For each model, an effect ratio (defined as the ratio of the indirect effect to the total effect, yielding the proportion of the effect that is mediated) and its bootstrapped distribution will be computed to assess the strength of mediation. Mediators (M) to be tested are improvements in health behaviors and self-efficacy. For example, we will analyze the effect of the intervention on change in maternal self-efficacy from baseline to Time 2, and, in turn the effects of this change in maternal self-efficacy at Time 2 on change in maternal BMI at Time 3.

Sensitivity analyses for Aims 1-3. Site will be included in all the models, and we will look for evidence of differential effects across cohort or site. The primary analyses use all available data, but if there is evidence of differential missingness by treatment group, we will use imputation methods as a sensitivity analysis.

Aim 4: We will calculate the incremental cost-effectiveness of the intervention, carried out from society's perspective as:

$$CE_{ij} = \frac{C_i - C_j}{E_i - E_j}$$

Where C is cost over the time period of the study; E is effectiveness measured by the outcomes; *i* refers to the intervention and *j* refers to the control group. We will calculate cost-effectiveness for the principal outcomes of the study; including cost per unit of BMI reduction, and cost per unit of improvement on the nutrition and physical activity self-efficacy scales. We will carefully track and calculate the costs of the program intervention activities and the control group activities, in order to measure the differences between the costs in the two groups. These costs will include hiring interventionists for all aspects of the Healthy Mothers-Healthy Children intervention. We will track the time invested in the program by participants in both the intervention and control group and calculate the value of time (opportunity cost) relative to the mothers' average income.

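### Aim 3 models each mediator separately, so a candidate that the intervention also moves and that correlates with a true mediator is credited with part of its effect

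*Combined protocol and SAP*

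**What the plan says.** Sections 3 and 9.1 give the purpose of Aim 3: "Identify the mediators through which the intervention influences the trajectory of adiposity and weight gain in children", and likewise for mothers. Section 9.4.10 repeats it as "To identify the mediators through which the intervention influences weight management in mother-child dyads".

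The models are specified per outcome and "for each proposed mediator (M), relative to the randomized intervention group (X). For each model, an effect ratio" follows, defined as indirect effect over total effect. For that ratio, "its bootstrapped distribution will be computed to assess the strength of mediation". The candidates are listed thus: "Mediators (M) to be tested are improvements in health behaviors and self-efficacy". The schedule in section 8.1 shows six such measures for mothers: two behavior questionnaires, food recall, accelerometry, an eating self-efficacy scale and the "Exercise Self-Efficacy Scale". The one worked example has a single mediator, self-efficacy, and considers "the effects of this change in maternal self-efficacy at Time 2 on change in maternal BMI at Time 3".

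The only additions to these models are site, imputation as a sensitivity analysis (9.4.10) and covariates found imbalanced at baseline (9.3). None adjusts one mediator for another. Section 9.2 says that for Aim 3 "the focus is on estimation (rather than testing) of direct and indirect mediation effects". No rule for declaring a mediator is stated.

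**The concern.** Aim 3 asks which component carries the effect: self-efficacy, diet or activity. A model with one mediator cannot separate them. If the intervention moves two correlated candidates and only one affects the outcome, the other stands in for it whenever it is modeled alone.

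The main condition, that the non-mediator is itself moved, is the plan's own hypothesis, since sections 3 and 9.1 expect all these measures to improve. Measuring the mediator at Time 2 and the outcome at Time 3 fixes their time order. It does not remove confounding by another mediator measured at the same visit.

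At stake is the attribution. Followed as written, Aim 3 may credit several candidates with shares of the effect that partly count the same thing.

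**Working it through.** **The plan's own figures.** There is no false-positive figure for Aim 3 to reproduce. The section 9.2 power figures do reproduce. A two-degree-of-freedom time-by-treatment test with 125 per arm and equal effects at Times 2 and 3 gives .950 for mothers, .987 for children and .832 in the pessimistic case (stated: above 95%, 95% and 80%).

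**Inputs.** From section 9.2: 125 per arm, and total effects of .45 (pessimistic) and .53 (mothers' pilot). Assumed, because the documents give no values: 
- intervention effect on the true mediator M1, a1 = .5 SD; 
- M1-to-outcome coefficient b1 = .30; 
- effect on the non-mediator M2, a2 = 0 to .5 SD; 
- residual M1-M2 correlation r = .3, .5, .7, wholly non-causal; 
- unit residual variances; 
- a mediator counts as credited when its 95% interval excludes zero.

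**Step 1: the spurious path.** Regressing the outcome on arm and M2 alone gives M2 a coefficient of b1 × r = .09, .15, .21, although its true coefficient is 0.

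**Step 2: hand approximation.** The interval for a2 × b excludes zero roughly when both paths are significant.
- a path: SE = √(2/125) = .1265. For a2 = .5, z = 3.95 and power is .977. For a2 = .2, z = 1.58 and power is .353. For a2 = 0 the rate is .05.
- b path: SE = √[(1 + .09(1 − r²))/250] = .0658, .0653, .0647. So z = 1.37, 2.30, 3.25 and power is .277, .631, .901.
- Products at r = .3 / .5 / .7: a2 = .5 gives 27 / 62 / 88%; a2 = .2 gives 10 / 22 / 32%; a2 = 0 gives 1 / 3 / 5%.

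**Step 3: simulation** (1,000 trials, 500 percentile-bootstrap resamples, direct effect .2, so total effect .2 + .5 × .30 = .35), indirect effect of M2:

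| a2 | r = .3 | r = .5 | r = .7 |
|---|---|---|---|
| .5 | 31% | 65% | 89% |
| .35 | 22% | 51% | 72% |
| .2 | 8% | 21% | 32% |
| 0 | 1% | 3% | 5% |

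A separate run at total effect .45 and a2 = .5 gave about 29 / 60 / 85%. With r = 0 and a2 = .5 the rate is 6%.

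**Step 4: the planned statistic.** For the effect ratio at a2 = .5, the rate also depends on the total effect:

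| Total effect | r = .3 | r = .5 | r = .7 |
|---|---|---|---|
| .15 (no direct effect) | 4% | 12% | 22% |
| .35 | 22% | 48% | 70% |
| .45 | 27% | 56% | 79% |
| .53 | 25% | 58% | 85% |
| .55 | not run | 63% | 89% |

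**Step 5: bias without any test.** At total effect .45 and a2 = .5, M1's true share is .5 × .30/.45 = .33. M2's true share is 0, but its single model gives .5 × .30 × r/.45 = .10, .17, .23. The two reported shares sum to .43, .50, .57, against .33 actually mediated.

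**Step 6: joint model.** With M1 and M2 together, M2's specific indirect effect excludes zero in about 3-8% of trials across the runs at a2 = .5, and 1-2% at a2 = .2.

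**Step 7: a serial naming rule.** Suppose self-efficacy is placed before behavior and named a mediator if either its specific or its serial effect excludes zero. Let behavior be the only true mediator. The model then reads the residual correlation as a self-efficacy-to-behavior path. All three serial paths are significant with probability about .977 × .999 × .995 = .97 at r = .3. By the same calculation it is .96 at r = .5 and .90 at r = .7. Two simulations of the rule gave 97 / 95 / 88% and 97 / 96 / 91%, against 25 / 62 / 87% for the single-mediator model.

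**The case against.** **Aim 3 is estimation.** Section 9.2 says so, and section 9.4.10 uses the ratio to gauge strength, with no decision rule. This stands against any claim that a 5% error rate is breached: the interval-excludes-zero rule is an assumption of this check. It does not rescue the estimates, which are biased and overlap (step 5). The plan also speaks of identifying mediators and of mediators to be tested.

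**The bootstrap is on a product.** A reader might infer that the planned analysis tests only association with the outcome, so that any correlated non-mediator is declared in 30-90% of trials. The documents do not support that. The indirect effect needs both paths, and a candidate that the intervention does not move is flagged in at most about 5% of trials.

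**The correlation may be causal.** If self-efficacy drives behavior, it is a genuine mediator and the single model is right to find it. This stands. The rates apply only to non-causal correlation. The documents list the two side by side in sections 3 and 9.1 and state no order.

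**Everything rests on assumed paths.** This is true, and for the effect ratio the rate runs from 4% to 89%. The lowest values need a total effect of .15, one third of the plan's pessimistic .45.

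**A joint model has limits.** It handles only measured mediators and costs precision. Both points stand. The primary tests in Aims 1 and 2 are unaffected.

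**Conclusion.** The concern holds with conditions. One model per mediator credits part of the effect to a candidate that the intervention also moves and that correlates non-causally with a true mediator. With 125 per arm, b1 = .30 and residual correlation .3 to .7, its indirect-effect interval excludes zero in roughly 30-90% of trials for a .5 SD shift, 8-32% for .2 SD, and no more than about 5% for no shift.

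These rates illustrate assumed paths; they are not departures from an error rate stated in the plan. What does not depend on a decision rule is that the separate proportions mediated are biased and overlap, so adding or ranking them is not justified. As written, Aim 3 cannot say which component carries the effect.

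**What to change.** In section 9.4.10, Aim 3:
- Add one joint model per outcome containing the Time 2 changes in the self-efficacy, nutrition and physical activity measures together. Bootstrap each specific indirect effect, and base any statement about which component carries the effect on these.
- Keep the single-mediator effect ratios, labelled as overlapping and not isolating separate pathways.
- Do not name a mediator on a serial self-efficacy-to-behavior path alone. Both are measured at Time 2, so the data cannot identify their order, and step 7 shows such a rule doing worse than the planned models. Report any serial path as exploratory, with the order assumption stated.

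The change needs SAP wording and modest programming, with no new data or participants. Intervals widen: at correlation .7, power for the true mediator falls from about 96% to about 87-91% with two mediators, and to about 80% with four to six. A specific effect omits any influence of self-efficacy that runs through behavior. Confounding by unmeasured variables remains, and the SAP should say so.

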6.3 MEASURES TO MINIMIZE BIAS: RANDOMIZATION AND BLINDING

After enrollment and baseline assessment, dyads will be randomized to either the intervention or control group using a computer-generated randomization table, stratifying by BMI group, overweight ($25 - 29.9 \text{ kg/m}^2$) and obese ($\geq 30 \text{ kg/m}^2$), and utilizing blocking to help ensure balance between the groups. Mothers will be informed of their group assignment by telephone. We have not included fathers, as in previous studies in this population, because the majority of fathers work 6 days a week and cannot attend class [7, 23]. Data collection research assistants will be blinded to group status.

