Exploratory Aim: Analyses will be performed on weight status, adiposity, health behavior, and self-efficacy to explore whether the intervention effects for mothers are similar for those who are overweight (BMI 25-29.9kg/m²) and those who are obese (BMI ≥ 30 kg/m²). The mixed models described for Aims 1 and 2 will be implemented for each of the weight status, adiposity, health behavior, and self-efficacy variables, with the addition of four explanatory variables to each model: an indicator for the obese group, the interaction between this indicator and the indicator variable for group membership, the interaction between this indicator and time, and the three-way interaction among the group indicator, obese indicator, and time. The hypothesis test for the three-way interaction as well as the obesity indicator by group indicator interaction jointly equal to zero will indicate whether the intervention effects are homogeneous across BMI ranges. For each outcome, differences will be calculated to test the effects of the intervention versus control group at each follow-up point separately for each BMI range. Similar analyses will be performed with groupings of children in the 25th-84.9th percentile (normal weight), 85th-94.9th percentile (overweight) and $\geq 95^{\text{th}}$ percentile (obese).

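### The exploratory homogeneity test by BMI group includes the pre-randomisation arm difference, so a rejection does not by itself show that intervention effects differ

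*Combined protocol and SAP*

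**What the plan says.** Section 9.4.10, Aim 1, defines the mixed model: "The dependent variable will be the outcome at each of the three time points", and "the model will include time point (categorical), intervention group, and the interaction between the two". Of the group-by-time interaction it says: "A test of this interaction will serve as the overall test of intervention effect". Aim 2 uses the same form for mothers.

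The Exploratory Aim adds four terms to these models: "an indicator for the obese group, the interaction between this indicator and the indicator variable for group membership", then obese by time, and obese by group by time. The decision rule is "The hypothesis test for the three-way interaction as well as the obesity indicator by group indicator interaction jointly equal to zero", which "will indicate whether the intervention effects are homogeneous across BMI ranges". The plan then compares the arms at each follow-up point within each BMI range. It applies the same approach to three child weight groups.

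On timing, Section 6.3 states: "After enrollment and baseline assessment, dyads will be randomized to either the intervention or control group". Allocation is stratified by the mother's BMI group, "utilizing blocking to help ensure balance between the groups". The imbalance check in Section 9.3 names gender, age and income. It does not name the baseline value of the outcome.

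**The concern.** Because Time 1 is one of the three responses, setting both interactions to zero says that the arm difference is the same in obese and overweight mothers at Time 1, Time 2 and Time 3. The Time 1 part was fixed before anyone was allocated. It reflects chance and carries no intervention effect, yet it can push the statistic over its critical value. The plan would then report effect modification where there is only a pre-treatment imbalance.

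The rule also departs from the plan's own definition of effect. The overall test for Aims 1 and 2 uses group by time only and leaves the group term out. The same problem arises for the child weight groups, where the joint null has 2 + 4 = 6 df, two of them baseline contrasts.

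**Working it through.** **Inputs.** From Section 9.2: 125 analysable dyads per arm, two-sided .05, correlation and standardised difference of .25 and .53 (mothers' BMI), .30 and .59 (children's BMI percentile), and .20 and .45 (lower scenario). Assumed, because the documents do not give them: half the mothers obese, so about 62 per arm-by-BMI cell; compound symmetry; effect pattern (0, d, d); any correlation above .30.

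**The plan's own figures.** 250/0.85 = 294.1, which agrees with 294. For the group-by-time F test, non-centrality = (n/2) × Σ(d_t − mean d)²/(1 − r), and Σ(d_t − mean d)² = 2d²/3 for (0, d, d):

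- .53, r = .25: 62.5 × 0.1873/0.75 = 15.6, power 95.1%
- .59, r = .30: 62.5 × 0.2321/0.70 = 20.7, power 98.7%
- .45, r = .20: 62.5 × 0.1350/0.80 = 10.5, power 83.4%

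These agree with the stated >95%, >95% and >80%. The plan gives no figure for the homogeneity test.

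**What the joint test contains.** Let b1, b2, b3 be the obese-minus-overweight difference in the arm difference at Times 1 to 3. The planned statistic is b′Σ⁻¹b on 3 df, critical value 7.815. In a simulated data set it had the same value with Time 1 as reference, with Time 3 as reference and with effect coding. The baseline component is therefore not an artefact of coding.

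**Conditional error with no effect modification.** The statistic splits into z² for the baseline contrast plus an independent 2-df chi-square for (b2, b3) given b1. The rejection probability given baseline z is P(χ²₂ > 7.815 − z²), at any correlation:

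- z = 0: P(χ²₂ > 7.815) = 2.0%
- z = 2.0: P(χ²₂ > 3.815) = 14.8%
- z = 2.5: P(χ²₂ > 1.565) = 45.7%
- z of about 2.80: the baseline term alone reaches 7.815

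The standard error of b1 is √(4/62) = 0.254 SD, so z = 2.0 and 2.5 are differences of 0.51 and 0.635 SD. Two-sided normal tails give P(|z| > 2.0) = 4.6% and P(|z| > 2.5) = 1.2%. Averaged over randomisation, the joint test rejects 5.0% of the time. About 37% of those false rejections come with |z| > 1.96, which occurs in 5% of trials.

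**Alternatives under the same imbalance.**

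| Test | z = 2.0 | z = 2.5 |
|---|---|---|
| Planned joint, 3 df | 15% | 46% |
| Three-way only, unconstrained, 2 df, r = .25 | 15% | 27% |
| Baseline constrained or adjusted, 2 df | 5% | 5% |

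At an assumed r = .9 the unconstrained three-way test rejects in 7.7% at z = 2.5. It is sensitive at low correlation because change from baseline then carries strong regression to the mean.

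**Power.** With v = 4/62 (in SD² units) and pattern (0, d, d), the planned and the constrained tests share non-centrality 2d²/[v(1 − r)(1 + 2r)]. The unconstrained three-way test has (2/3)d²/[v(1 − r)]. The ratio is 3/(1 + 2r), which is 2 at r = .25. At each correlation, d is scaled so that the unconstrained test has power .36 (non-centrality 3.40). At r = .25 this gives d² = 3.40 × 1.5 × 0.75 × 0.0645 = 0.247, so d is about 0.50 SD.

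| r | Unconstrained, 2 df | Planned, 3 df | Constrained, 2 df |
|---|---|---|---|
| .25 | .36 | .58 | .64 |
| .5 | .36 | .45 | .51 |
| .8 | .36 | .35 | .41 |
| .9 | .36 | .33 | .38 |

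**The case against.** The strongest reply is that the test is valid. Randomisation makes the baseline contrast zero in expectation, and the 5% level holds overall. A reader might infer that the plan will find false effect modification more often than it should; the calculations do not support that. The 46% figure is conditional on an imbalance that about 1 test in 80 reaches or exceeds.

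A reader might also infer that the subgroup test should simply copy the main analysis and use the three-way term alone. At the plan's correlation of .25 that version reacts to a baseline imbalance of z = 2.0 just as much and is clearly less powerful than the planned test. When post-baseline effects do differ, the baseline contrast carries information, so the third degree of freedom is not mere waste.

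The plan also estimates arm differences at each follow-up within BMI range, and Aim 1 reports group means at every time point. If those are carried into the subgroup models, an imbalance would be visible.

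All of this stands, and it limits the point. It does not repair the statement of what a rejection will show. Nothing in the plan constrains or adjusts for the baseline outcome, and stratifying by BMI group balances numbers within strata, not outcome values. Child weight group is not a stratification factor at all.

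**Conclusion.** The point holds in a limited form. The planned test mixes a pre-randomisation contrast with the post-baseline ones, so a rejection is not by itself evidence that intervention effects differ by BMI group. The harm is to interpretation, to error after an observed baseline imbalance, and modestly to power (.58 against .64 at r = .25).

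The conditional rejection rates of the planned test do not depend on the correlation. The power figures rest on 62 mothers per cell, compound symmetry, the (0, d, d) pattern and a chosen effect size; only correlations of .20 to .30 come from the plan. The advantage of the constrained test appears at every correlation examined and comes from the baseline constraint, not from dropping a term. The aim is exploratory and carries no stated power or error claim, so the primary conclusions are untouched. This is a minor improvement.

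**What to change.** In the Exploratory Aim, state that arm means are constrained to be equal at Time 1 within each BMI group. One way is to fit obese, time and obese by time, with arm terms at Time 2 and Time 3 only and their interactions with obese. Adjusting for the baseline outcome is an acceptable alternative. Define homogeneity as the post-baseline arm-by-BMI-group terms being jointly zero: 2 df for mothers, and 4 df for the three child weight groups. Do not merely remove obese by group from the planned test.

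No new data or participants are needed. The cost is that the exploratory model will differ in its baseline parameterisation from the Aim 1 and 2 models, and the plan should say so and give the reason.
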